9.3.3 Urinary Hex4

Fasted urine samples for the assessment of urinary Hex4 concentrations will be collected prior to IMP infusion. Procedures for the collection, handling, and shipment of all urine samples will be included in the study-specific laboratory manual.

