11.4 PATIENT DEMOGRAPHIC AND MEDICAL HISTORY

Medical/surgical history, and Pompe disease history, including GAA gene mutations, will be imported from the patient's prior avalglucosidase alfa study file in the database when possible. ECG, hematology, biochemistry, and urinalysis data from first day of avalglucosidase alfa infusion (ie, prior to first infusion in any prior avalglucosidase alfa study) will be entered by the study site into the database. These data will be summarized using summary statistics for continuous variables and frequency distribution for categorical variables. All data will be presented in by-patient listings.

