2 STATISTICAL AND ANALYTICAL PROCEDURES

The statistical analysis and reporting will be based on all data from study TDR12857 and its extension study, LTS13769. The baseline value is defined as the last non missing value prior to first TDR12857 treatment, unless otherwise specified. The rebaseline values will be the last non-missing assessment before patients switch to 20 mg/kg dose for LTS-switch patients.

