Appendix B Visit windows

The analysis visits are assigned by comparing the distance between the calculated study day of each assessment (defined as time elapsed from the start of study drug in the TDR12857 study till the time of the assessment) with the listed target study days and the corresponding analysis windows of the applicable group of assessments, utilizing the general rules below:

1. If more than one non-missing values are assigned to the same analysis visit, then the assessment performed closest to the target study day will be used in the by-visit analysis.
2. Multiple values assessed on the same date will be averaged prior to being assigned an analysis visit.
3. If two assessments are assessed on different dates but equidistant from the target date, the values assessed on a later date will be used.
4. Use a combination of 2 & 3 in cases where there are multiple records equidistant from the target study day. For example, for a post-baseline visit, if there are 2 records, 7 days before the infusion and 3 records 7 days after the infusion, then take the 3 records after the infusion and average them for analysis value.

All visits in the applicable datasets will be used, including scheduled and unscheduled visits. (For change from TDR12857 baseline analyses, rebaseline visit and assessments performed after rebaseline will be handled in the same manner.) Note that baseline is defined as the latest available observation before the first infusion in the TDR12857.

Table 1 — Analysis windows for 6MWT, PFTs, ECG, hematology, and urinalysis:

VISIT (target study day*)	Analysis Visit	Analysis Visit Window (in study days*)
Baseline	Baseline	
Week 1@ in TDR (1)	Week 1	1 to 42 days
Week 13 in TDR (85)	Week 13	43 to 127 days
Week 25 in TDR (169)	Week 25	128 to 273 days/(1 st day of LTS – 1)**
Month 6 in LTS (365)	Week 52	(1 st day of LTS) to 456 days
Month 12 in LTS (547)	Week 78	457 to 638 days
Month 18 in LTS (730)	Week 104	639 to 821 days
Month 24 in LTS (912)	Week 130	822 to 1003 days
Month 30 in LTS (1095)	Week 156	1004 to 1186 days
Month 36 in LTS (1277)	Week 182	1187 to 1368 days
Month 42 in LTS (1460)	Week 208	1369 to 1551 days
Month 48 in LTS (1642)	Week 234	1552 to 1733 days
Month 54 in LTS (1825)	Week 260	1734 to 1916 days
Month 60 in LTS (2007)	Week 286	1917 to 2098 days
Month 66 in LTS (2190)	Week 312	2099 to 2281 days
Month 72 in LTS (2372)	Week 338	2282 to 2402 days

@ Week 1 visit only applies to ECG, hematology, and urinalysis.

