*Study days are days since the first infusion in the TDR12857 study.

**For patients who enrolled in LTS13769, the upper boundary of the window is 273 days or (1st day of LTS – 1), whichever is earlier; for patients who didn't enroll in LTS13769, use study day 273 as cutoff.

Table 2 – Immunogenicity (anti-alglucosidase alfa IgG antibody) – Group 2 patients only

VISIT (target study day*)	Analysis Visit	Analysis Visit Window (in study days*)
Baseline/Week 1	Baseline	
Week 25 in TDR (169)	Week 25	92 to 273 days/(1 st day of LTS – 1)**
Month 6 in LTS (365)	Week 52	(1 st day of LTS) to 456 days
Month 12 in LTS (547)	Week 78	457 to 638 days
Month 18 in LTS (730)	Week 104	639 to 821 days
Month 24 in LTS (912)	Week 130	822 to 1003 days
Month 30 in LTS (1095)	Week 156	1004 to 1186 days
Month 36 in LTS (1277)	Week 182	1187 to 1368 days
Month 42 in LTS (1460)	Week 208	1369 to 1551 days
Month 48 in LTS (1642)	Week 234	1552 to 1733 days
Month 54 in LTS (1825)	Week 260	1734 to 1916 days
Month 60 in LTS (2007)	Week 286	1917 to 2098 days
Month 66 in LTS (2190)	Week 312	2099 to 2281 days
Month 72 in LTS (2372)	Week 338	2282 to 2402 days

*Study days are days since the first infusion in the TDR12857 study.

**For patients who enrolled in LTS13769, the upper boundary of the window is 273 days or (1st day of LTS – 1), whichever is earlier; for patients who didn't enroll in LTS13769, use study day 273 as cutoff.

Table 3 – Immunogenicity (anti-avalglucosidase alfa [neoGAA] antibodies)

VISIT (target study day*)	Analysis Visit	Analysis Visit Window (in study days*)
Baseline/Week 1	Baseline	
Week 5 in TDR (35)	Week 5	23 to 50 days
Week 9 in TDR (63)	Week 9	51 to 78 days
Week 13 in TDR (91)	Week 13	79 to 106 days
Week 17 in TDR (119)	Week 17	107 to 134 days
Week 21 in TDR (148)	Week 21	135 to 163 days
Week 25 in TDR (176)	Week 25	164 to 183 days
Week 27 in TDR (190)	Week 27	184 to 198 days/(1 st day of LTS - 1)
Month 1 in LTS (213)	Week 32	(1 st day of LTS) to 228 days
Month 2 in LTS (244)	Week 36	229 to 259 days
Month 3 in LTS (274)	Week 40	260 to 289 days
Month 4 in LTS (304)	Week 44	290 to 319 days
Month 5 in LTS (335)	Week 48	320 to 350 days
Month 6 in LTS (365)	Week 52	351 to 411 days
Month 9 in LTS (456)	Week 65	412 to 502 days
Month 12 in LTS (547)	Week 78	503 to 594 days
Month 15 in LTS (639)	Week 91	595 to 685 days
Month 18 in LTS (730)	Week 104	686 to 776 days
Month 21 in LTS (821)	Week 117	777 to 867 days
Month 24 in LTS (912)	Week 130	868 to 959 days

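### In SAP Appendix B Tables 1, 4 and 5 the first-day pre-infusion value can be both Baseline and Week 1, making the Week 1 change zero or diluted

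*SAP*

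**What the plan says.** **Baseline.** SAP section 2: "The baseline value is defined as the last non missing value prior to first TDR12857 treatment, unless otherwise specified". Appendix B repeats the rule: "Note that baseline is defined as the latest available observation before the first infusion in the TDR12857".

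**When the baseline sample was taken.** Protocol 11.4 describes the imported values as "ECG, hematology, biochemistry, and urinalysis data from first day of avalglucosidase alfa infusion (ie, prior to first infusion in any prior avalglucosidase alfa study". For Hex4 there is only the LTS13769 rule in Protocol 9.3.3: "Fasted urine samples for the assessment of urinary Hex4 concentrations will be collected prior to IMP infusion".

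**Week 1.** Appendix B Tables 1, 4 and 5 each list a Baseline row and a separate Week 1 row with target day 1. The Week 1 window is days 1 to 42 in Table 1 and days 1 to 8 in Table 4 (biochemistry) and Table 5 (Hex4). In Table 1, "Week 1 visit only applies to ECG, hematology, and urinalysis". Tables 2 and 3 (antibodies) instead have one combined row, "Baseline/Week 1".

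**Selection rules.** Rule 1 keeps the value nearest the target day. Rule 2 averages values from the same date before a visit is assigned. Scheduled and unscheduled records are all eligible, and no exclusion of pre-infusion records is stated.

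**Study day.** Appendix B says "defined as time elapsed from the start of study drug in the TDR12857 study till the time of the assessment"; the table footnotes say "Study days are days since the first infusion in the TDR12857 study".

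**The concern.** A value that serves as Baseline should not reappear as a post-baseline result. If it does, part or all of the Week 1 change is a value minus itself. The row then looks like evidence of stability after the first infusion when it carries no such information.

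Safety is the primary endpoint, and the affected outputs are planned ones:

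- by-visit changes for all laboratory variables, and mean-change plots with standard errors for ALT, AST, creatinine, CK and CK-MB (SAP 2.4.5.3);
- by-visit ECG changes (SAP 2.4.5.5);
- Hex4 changes with 95% confidence intervals (SAP 2.4.7), if the sampling assumption holds.

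Because the definition of study day and the target days disagree, two programmers following the SAP could also produce different Week 1 rows.

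**Working it through.** **1. Which day number does the first infusion date carry?** Compare the listed TDR12857 targets for week w with 7(w−1)+1 (infusion date = day 1) and 7(w−1) (infusion date = day 0).

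- Table 1: Weeks 1, 13 and 25 have targets 1, 85 and 169. 7(w−1)+1 gives 1, 85 and 169, so 3 of 3 match. 7(w−1) gives 0, 84 and 168, so none match.
- Tables 4 and 5: targets are 1, 15, 29, 43, 57, 71, 85, 99, 113, 127, 142, 156 and 169. 7(w−1)+1 matches 11 of 13; Weeks 21 and 23 are one day later (142 against 141, 156 against 155). 7(w−1) matches none.

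In these three tables the infusion date is therefore day 1. Table 3 follows another pattern (35, 63, 91 and 119 are 7w for Weeks 5, 9, 13 and 17), but it has no separate Week 1 row.

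**2. Where does the pre-infusion sample fall?** Its day is 1, inside both 1–42 and 1–8. Its distance from the target is |1−1| = 0, so under rule 1 no later value in the window can displace it.

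**3. What results?** Apply the rules to invented values (illustration only), with a screening value of 100 in every case. The last column applies the proposed rule.

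| Further records | Baseline | Week 1 value | Change | Change after fix |
|---|---|---|---|---|
| Day-1 pre-infusion 110 | 110 | 110 | 0 | empty |
| Day-1 pre-infusion 110; day 6, 150 | 110 | 110 | 0 | 150−110 = +40 |
| Day-1 pre-infusion 110; day-1 post-infusion 130 | 110 | (110+130)/2 = 120 | +10 | 130−110 = +20 |
| No day-1 sample; day 6, 150 | 100 | 150 | +50 | +50 |

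In Table 1 a day-20 value in place of day 6 is passed over in the same way. If a fraction p of patients contribute structural zeros and the rest have mean change δ, the row mean is (1−p)δ. The documents do not give p; over its range of 0 to 1 the row mean runs from δ to 0.

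**4. What if elapsed time is taken literally?** A pre-infusion sample then has negative study time and misses the window. The first case gives an empty Week 1 and the second gives +40. A post-infusion sample taken within a day of the start of infusion also falls below 1 and is lost, so the third case is empty too. Week 1 would then exclude samples from the very date that is its target. Table 6 (plasma concentration) would share the problem: its Week 1 target is day 1 and its window is 1–42, so samples taken within a day of starting the first infusion would fall outside it.

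**5. Which other samples can be pushed out?** After Week 1, the next listed target is day 85 in Table 1 and day 15 in Tables 4 and 5. No visit is listed on days 2–42 or days 2–8 respectively, so only unscheduled or off-schedule samples can lose the slot.

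**The case against.** The strongest reply is that the SAP, read as written, already excludes the pre-infusion sample: study day runs from the start of drug, so an earlier sample cannot reach a window opening at day 1. SAP 2.4.5.3 and 2.4.5.5 also distinguish baseline from post-baseline time points, so a sensible programmer would not count one record as both. This does not settle the matter. The elapsed-time reading contradicts the targets in the affected tables and empties Week 1 of its own target date. The distinction in section 2.4.5 is not turned into any assignment rule.

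Other parts of the reply stand:

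- A reader might infer that every patient with a day-1 pre-infusion sample shows a Week 1 change of exactly 0, and that the row has SD 0 and a confidence interval of 0 to 0. The documents do not support this. Rule 2 averages in any same-day post-infusion value, and a patient with no day-1 sample can contribute a real change.
- A reader might also infer that scheduled early safety data are lost. No scheduled visit is listed in those days. SAP 2.5.5 already uses unscheduled laboratory and ECG values in by-visit summaries only when the scheduled value is unavailable. SAP 2.4.5 still counts them for PCSAs.
- The TDR12857 sampling schedule is not in the documents. Protocol 11.4 supports the timing for ECG and safety laboratory data but does not mention Hex4, and it does not say whether post-infusion samples were also taken that day.
- Merging Week 1 into Baseline and stopping there would leave early post-infusion values without an analysis visit. Tables 2 and 3 have that gap: their first post-baseline windows open on day 92 and day 23.

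**Conclusion.** The point holds in a limited form. Under the numbering that the targets imply, the first-day pre-infusion ECG, hematology, urinalysis and biochemistry value is both Baseline and the selected Week 1 value. The Week 1 change is zero by construction where that is the only day-1 value, and attenuated where a same-day post-infusion value is averaged with it (halved with one value of each kind). Separately, the stated definition of study day conflicts with the targets.

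The size is small: the Week 1 rows of descriptive by-visit tables and the first points of the mean-change plots. 6MWT and PFT have no Week 1 row, and later visits and PCSA counts do not change.

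The conclusion rests on two assumptions: that study days are counted by date with the first infusion date as day 1 (inferred from the targets, not stated), and, for Table 5 only, that Hex4 was sampled before infusion in TDR12857 as it is in LTS13769.

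**What to change.** In SAP Appendix B:

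1. Define study day as assessment date minus first TDR12857 infusion date + 1, for dates on or after the first infusion, and align the footnotes.
2. State that a record taken before the start of the first infusion is assigned only to Baseline. It never enters a post-baseline window and is never averaged with a post-infusion value from the same date. Carry the same exception into the same-day averaging text in SAP 2.5.3 and 2.5.5.
3. In Tables 1, 4 and 5, label the scheduled day-1 pre-infusion visit "Baseline/Week 1", as in Tables 2 and 3.
4. Keep a post-baseline window (days 1–42 in Table 1, days 1–8 in Tables 4 and 5) for post-infusion values only, left empty if there are none.

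The cost is a few lines of appendix and data-handling text and one programming condition that separates pre- from post-infusion records on day 1. No new data are needed.

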10.1 VISIT SCHEDULE

10.1.1 Baseline visit

Patients enrolled in the study will have the following procedures performed at baseline.

The patient will receive information on the study objectives and procedures from the Investigator. The patient will have to sign the informed consent prior to any action related to the study.

Patients who meet all the inclusion criteria and none of the exclusion criteria will be eligible for inclusion in the study. Final inclusion will be performed just before the IMP administration at the first treatment visit.

- Informed consent.
- Inclusion/exclusion criteria.
- Urine pregnancy test (females only).
- ECG.
- Demographics.
- Medical/Surgical history.
- Pompe disease history, inclusive of GAA mutation and aspects of disability.
- ECG, hematology, biochemistry, and urinalysis data from first day of avalglucosidase alfa infusion (ie, prior to first infusion in any prior avalglucosidase alfa study).
- Results of MRI baseline from previous avalglucosidase alfa study to be obtained.

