10.1.2.4 Every 6 months

The following assessments will be performed every 6 months:

- Physical examination.
- ECG.
- Hematology and urinalysis.
- 6MWT.
- PFT.
- Anti-alglucosidase alfa IgG antibodies (only patients who were previously treated with alglucosidase alfa).

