2.1.3.2 Secondary efficacy endpoint(s)

The exploratory efficacy endpoints include the six-minute walk test (6MWT) and the pulmonary function testing (PFT). These assessments were performed at baseline, Week 13, and Week 25 in the TDR12857 study, at the baseline for roll over to LTS 13769, and performed every 6 months, at the rebaseline visit (for patients previously in the 5 and 10 mg/kg dose groups only; see [Section 1.4](#)), and at the end of study visit in the LTS13769 study.

Six-minute walk test (6MWT)

The 6MWT assessments include: the distance walked in 6 minutes, measured in meters; the percentage of predicted distance; and the amount of time walked to quantify endurance (as all patients may not complete the full 6-minute walk). In addition, data will be collected for pretest versus posttest changes in heart rate and assistive device use. The distance (in meters) will be recorded and the corresponding percentage of predicted value will be calculated. The percentage of predicted distance walked will be calculated based on the normal reference equation in [Table 1](#). For analysis purposes, the age at each assessment will be calculated based on (assessment date - birth date + 1)/365.25.

Table 1 - Equations for calculating reference value for percentage of predicted total distance walked in 6MWT (1)

Age at baseline	Gender	Equation
≥18 years	Male and Female	868.8 - 2.99 * age - 74.7 * sex

Age in years; sex = 0 if male and sex = 1 if female.

In order to compare the percent predicted values with studies using several percent predicted equations, the percentage of predicted distance walked will be calculated based on the normal reference equation in [Table 2](#). For analysis purposes, the age at each assessment will be calculated based on (assessment date - birth date + 1)/365.25, weight is collected at the time of the assessment and height will be baseline height for the study.

Table 2 - Equations for calculating reference value for percentage of predicted total distance walked in 6MWT (2)

Gender	Equation
Male	7.57*height (cm)-5.02*age (year)-1.76*weight (kg)-309
Female	2.11*height (cm)-5.78*age (year)-2.29*weight (kg)+667

Additional supportive analysis of 6MWT based on subjects who completed the full 6 minute walk by excluding subjects that walked less than 6 minutes will be provided.

Pulmonary function test

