Month 27 in LTS (1004)	Week 143	960 to 1050 days
Month 30 in LTS (1095)	Week 156	1051 to 1141 days
Month 33 in LTS (1186)	Week 169	1142 to 1232 days

VISIT (target study day*)	Analysis Visit	Analysis Visit Window (in study days*)
Month 36 in LTS (1277)	Week 182	1233 to 1324 days
Month 39 in LTS (1369)	Week 195	1325 to 1415 days
Month 42 in LTS (1460)	Week 208	1416 to 1506 days
Month 45 in LTS (1551)	Week 221	1507 to 1597 days
Month 48 in LTS (1642)	Week 234	1598 to 1689 days
Month 51 in LTS (1734)	Week 247	1690 to 1780 days
Month 54 in LTS (1825)	Week 260	1781 to 1871 days
Month 57 in LTS (1916)	Week 273	1872 to 1962 days
Month 60 in LTS (2007)	Week 286	1963 to 2054 days
Month 63 in LTS (2099)	Week 299	2055 to 2145 days
Month 66 in LTS (2190)	Week 312	2146 to 2236 days
Month 69 in LTS (2281)	Week 325	2237 to 2327 days
Month 72 in LTS (2372)	Week 338	2328 to 2402 days

*Study days are days since the first infusion in the TDR12857 study.

**For patients who enrolled in LTS13769, the upper boundary of the window is 273 days or (1st day of LTS – 1), whichever is earlier; for patients who didn't enroll in LTS13769, use study day 273 as cutoff.

Table 4 – Biochemistry

VISIT (target study day*)	Analysis Visit	Analysis Visit Window (in study days*)
Baseline	Baseline	
Week 1 in TDR (1)	Week 1	1 to 8 days
Week 3 in TDR (15)	Week 3	9 to 21 days
Week 5 in TDR (29)	Week 5	22 to 35 days
Week 7 in TDR (43)	Week 7	36 to 49 days
Week 9 in TDR (57)	Week 9	50 to 63 days
Week 11 in TDR (71)	Week 11	64 to 77 days
Week 13 in TDR (85)	Week 13	78 to 91 days
Week 15 in TDR (99)	Week 15	92 to 105 days
Week 17 in TDR (113)	Week 17	106 to 119 days
Week 19 in TDR (127)	Week 19	120 to 133 days
Week 21 in TDR (142)	Week 21	134 to 148 days
Week 23 in TDR (156)	Week 23	149 to 162 days
Week 25 in TDR (169)	Week 25	163 to 176 days/(1 st day of LTS – 1)**
Day 1/Week 0 in LTS (183)	Week 28	(1 st day of LTS) to 198 days
Month 1 in LTS (213)	Week 32	199 to 228 days
Month 2 in LTS (244)	Week 36	229 to 259 days
Month 3 in LTS (274)	Week 40	260 to 289 days
Month 4 in LTS (304)	Week 44	290 to 319 days
Month 5 in LTS (335)	Week 48	320 to 350 days
Month 6 in LTS (365)	Week 52	351 to 380 days
Month 7 in LTS (396)	Week 56	381 to 411 days
Month 8 in LTS (426)	Week 61	412 to 441 days

VISIT (target study day*)	Analysis Visit	Analysis Visit Window (in study days*)
Month 9 in LTS (456)	Week 65	442 to 471 days
Month 10 in LTS (487)	Week 69	472 to 502 days
Month 11 in LTS (517)	Week 74	503 to 532 days

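### In SAP Appendix B Table 1 the Week 52 window opens on the first LTS day, so a rollover ECG (and 6MWT or PFT, if done) can be reported as Week 52

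*SAP*

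**What the plan says.** **Which assessments are made at rollover.** SAP 2.1.3.2 lists 6MWT and PFT at baseline, Week 13 and Week 25 of TDR12857, then "at the baseline for roll over to LTS 13769", then six-monthly in LTS13769. Protocol 10.1.1 begins "Patients enrolled in the study will have the following procedures performed at baseline" and names an ECG, but neither 6MWT nor PFT. The flow chart in protocol 1.2.1 agrees with 10.1.1. Protocol 10.1.2.4 puts 6MWT, PFT and ECG under "The following assessments will be performed every 6 months".

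**How values are assigned to visits.** SAP Appendix B Table 1 counts study days from the first TDR12857 infusion. The row beginning "Week 25 in TDR (169" is analysis visit Week 25. For patients who enter LTS13769, "the upper boundary of the window is 273 days or (1st day of LTS – 1), whichever is earlier". The next row begins "Month 6 in LTS (365", is analysis visit Week 52, and has the window "1 st day of LTS) to 456 days". No row lies between the two. In the same appendix, Table 4 (biochemistry) does have such a row, beginning "Day 1/Week 0 in LTS (183" and labelled Week 28.

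**General rules.** Appendix B sends scheduled and unscheduled visits alike through the windows. Within a window the value closest to the target day enters the by-visit analysis, and a tie between dates goes to the later one. SAP 2.4.4.2 and 2.5.3 say that missing data are not imputed.

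**The concern.** Table 1 leaves no time between the end of Week 25 and the start of Week 52, whose target is about half a year later. A measurement made on the first LTS day belongs in time with Week 25 but is classed as Week 52. If nothing later is available in that window, Table 1 supplies a rollover value where Week 52 should be shown as missing.

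The stake is modest but concrete. ECG is part of the primary safety endpoint and is summarized by visit (SAP 2.4.5.5). For 6MWT and PFT, SAP 2.4.4.2 plans changes from baseline with 95% CIs at each visit. A value about 26 weeks from its label enters those summaries with nothing to mark it, and the patient is not counted as missing.

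**Working it through.** **1. Reproduce Table 1.** The LTS target days follow floor(182.5 × (m/6 + 1)) for LTS month m. Month 6 gives 182.5 × 2 = 365. Month 12 gives 182.5 × 3 = 547.5, so 547. Month 72 gives 182.5 × 13 = 2372.5, so 2372. All 12 targets are reproduced. The upper bounds are midpoints of adjacent targets, rounded down: (365 + 547)/2 = 456, and (2190 + 2372)/2 = 2281. All 11 bounds from 456 to 2281 are reproduced. The pattern implies LTS Day 1 at about day 182.5; Table 4 prints 183.

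**2. Place a value dated on the first LTS day.** Week 25 closes no later than the day before and Week 52 opens that day, so the value is in Week 52. Its distance from target is 365 − D, where D is the study day of LTS Day 1:

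| D | 365 − D (days) | Weeks |
|---|---|---|
| 170 | 195 | 27.9 |
| 183 (nominal) | 182 | 26.0 |
| 197 | 168 | 24.0 |
| 240 | 125 | 17.9 |
| 273 | 92 | 13.1 |

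**3. Apply the nearest-to-target rule.** With D = 183, a Month 6 value on day 365 ± 14 (351 to 379) is at most 14 days from target and replaces the rollover value. More generally, for D up to 274 any later value in the window replaces it. A value up to day 365 is closer, and one from 366 to 456 is at most 456 − 365 = 91 days off, against at least 365 − 274 = 91 for rollover, with a tie going to the later date. The rollover value is reported as Week 52 only if nothing later exists up to day 456.

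**4. Late rollover.** For D = 275, an on-schedule Month 6 value falls on 275 + 182 = 457, which is in Week 78. The rollover value is then reported as Week 52 although Month 6 was attended, 365 − 275 = 90 days (12.9 weeks) from target. Still later rollover narrows that gap.

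**5. Meaning of the first LTS day.** The SAP does not define it. If it is the first LTS infusion and the assessment was made the day before (day 182), the value falls in Week 25, 182 − 169 = 13 days (1.9 weeks) from target, and competes with the Week 25 value. For D of 275 or more, an assessment dated after day 273 but before the first LTS day has no window.

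**6. Share of Week 52 data.** Neither document gives the number of patients. One such value is 1/N of the Week 52 data. As assumed sizes only, N = 15 gives 6.7% and N = 30 gives 3.3%.

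**7. After the change.** With a row at target 183, the midpoint rule gives (183 + 365)/2 = 274. Week 28 runs from the first LTS day to 274, and Week 52 from 275 to 456. A rollover value on day 183 is then 0 days from target, and a Month 6 value on days 351 to 379 stays in Week 52.

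**The case against.** The strongest reply is that Table 1 matches the protocol for both efficacy measures. The protocol schedules no 6MWT or PFT at LTS baseline, so if sites followed it there is nothing to misplace and the error is the one clause in SAP 2.1.3.2. This stands as a reason to reconcile the documents. It does not cover the ECG, which the protocol does schedule at baseline.

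A second reply is that baseline assessments may precede the first LTS infusion and so fall in Week 25. That also stands, but it depends on a definition that the SAP does not give.

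A third is that Table 4's extra row proves little. Biochemistry is windowed two-weekly and then monthly, while the sparser Tables 2, 5 and 6 also go straight from Week 25 to Month 6. This is fair: Table 4 supplies a label and a nominal day, not proof of an oversight.

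Three stronger readings are tempting, and the documents do not support them:

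- **A mid-point of the time course is lost.** Week 25 (target day 169) is still reported, 183 − 169 = 14 days before nominal rollover.
- **Data are discarded.** The selection rule governs by-visit summaries only. The value stays in the dataset, and counts of potentially clinically significant ECG abnormalities use all evaluations in the treatment-emergent period (SAP 2.4.5). Changes from rebaseline use recorded visits and are unaffected.
- **Every missed Month 6 visit produces a mislabelled value.** A late or unscheduled assessment up to day 456 would take the rollover value's place.

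**Conclusion.** The concern holds in limited form. As written, Table 1 places an assessment dated on the first LTS day in Week 52, nominally 26 weeks from target and about 13 to 28 weeks for rollover between days 273 and 170. Where a value nearer day 365 exists, the effect is a small loss from the by-visit summaries. Where none exists up to day 456, a rollover value stands in for Week 52, which conflicts with the no-imputation rule.

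This rests on three assumptions: that the assessment is dated on or after the first LTS day, that nominal rollover is day 183 as in Table 4, and, for 6MWT and PFT, that SAP 2.1.3.2 describes what was done. The ECG part rests on the protocol schedule. How many patients are affected cannot be worked out from the documents. This is a minor correction to a table rule, not a threat to the study's conclusions.

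**What to change.** - In Table 1, add a row for LTS Day 1/Week 0, target day 183, analysis visit Week 28, window from the first LTS day to day 274. Apply it to ECG and, if collected, 6MWT and PFT. Table 4's row cannot be copied unchanged, because its window ends at day 198.
- Start the Week 52 window at day 275.
- Define the first LTS day as either the consent date or the first LTS infusion.
- State that a rollover assessment goes to Week 28 and never to Week 52, even if it falls after day 274. Week 52 may then be empty for a patient who rolled over late, and should be shown as missing.
- Reconcile SAP 2.1.3.2 with protocol 10.1.1 and the flow chart on whether 6MWT and PFT are done at rollover.

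The cost is one added row, one changed row and a few sentences, with no new data collection. The price is a Week 28 summary close in time to Week 25 and largely empty for hematology and urinalysis, which have no new sample scheduled at LTS baseline.

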Week 11 in TDR (71)	Week 11	64 to 77 days
Week 13 in TDR (85)	Week 13	78 to 91 days
Week 15 in TDR (99)	Week 15	92 to 105 days
Week 17 in TDR (113)	Week 17	106 to 119 days
Week 19 in TDR (127)	Week 19	120 to 133 days
Week 21 in TDR (142)	Week 21	134 to 148 days
Week 23 in TDR (156)	Week 23	149 to 162 days
Week 25 in TDR (169)	Week 25	163 to 176 days/(1 st day of LTS – 1)**
Month 6 in LTS (365)	Week 52	(1 st day of LTS) to 548 days
Month 18 in LTS (730)	Week 104	549 to 913 days
Month 30 in LTS (1095)	Week 156	914 to 1278 days
Month 42 in LTS (1460)	Week 208	1279 to 1643 days
Month 54 in LTS (1825)	Week 260	1644 to 2008 days
Month 66 in LTS (2190)	Week 312	2009 to 2373 days
Month 72 in LTS (2372)	Week 338	2374 to 2402 days

*Study days are days since the first infusion in the TDR12857 study.

**For patients who enrolled in LTS13769, the upper boundary of the window is 176 days or (1st day of LTS – 1), whichever is earlier; for patients who didn't enroll in LTS13769, use study day 176 as cutoff.

Table 6 – Plasma concentration of avalglucosidase alfa

VISIT (target study day*)	Analysis Visit	Analysis Visit Window (in study days*)
Baseline	Baseline	
Week 1 in TDR (1)	Week 1	1 to 42 days
Week 13 in TDR (85)	Week 13	43 to 127 days
Week 25 in TDR (169)	Week 25	128 to 273 days/(1 st day of LTS – 1)**
Month 6 in LTS (365)	Week 52	(1 st day of LTS) to 548 days
Month 18 in LTS (730)	Week 104	549 to 913 days
Month 30 in LTS (1095)	Week 156	914 to 1278 days
Month 42 in LTS (1460)	Week 208	1279 to 1643 days
Month 54 in LTS (1825)	Week 260	1644 to 2008 days
Month 66 in LTS (2190)	Week 312	2009 to 2373 days
Month 72 in LTS (2372)	Week 338	2374 to 2402 days

*Study days are days since the first infusion in the TDR12857 study.

**For patients who enrolled in LTS13769, the upper boundary of the window is 273 days or (1st day of LTS – 1), whichever is earlier; for patients who didn't enroll in LTS13769, use study day 273 as cutoff.

Table 7 –MRI, muscle biopsy

VISIT (target study day*)	Analysis Visit	Analysis Visit Window (in study days*)
Baseline	Baseline	
Week 27 in TDR (184)	Week 27	92 to 273 days/(1 st day of LTS – 1)**
Month 24 in LTS (365)	Week 52	(1 st day of LTS) to 1278 days
Month 48 in LTS (1095)	Week 156	1279 to 2008 days
Month 72 in LTS (2372)	Week 338	2009 to 2402 days

*Study days are days since the first infusion in the TDR12857 study.

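### SAP Appendix B Table 3 sets the TDR12857 antibody visits 6 to 7 days later than the other window tables, so a Week 27 sample drawn by day 183 is reported as Week 25 and can replace the true Week 25 titer

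*SAP*

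**What the plan says.** All Appendix B tables count study days from the first TDR12857 infusion. If several values fall in one analysis visit, rule 1 uses the one closest to the target day. For ties, rule 3 says that if two are "equidistant from the target date, the values assessed on a later date will be used".

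Table 3, for anti-avalglucosidase alfa antibodies, starts its on-treatment rows at "Week 5 in TDR (35" and ends its TDR12857 rows with:

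- "Week 25 in TDR (176", window "164 to 183 days";
- "Week 27 in TDR (190", window "184 to 198 days/(1 st day of LTS - 1".

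The number after the bracket is the target day. Elsewhere in Appendix B, Tables 1, 2, 4, 5 and 6 have "Week 25 in TDR (169" and Table 7 (MRI, biopsy) has "Week 27 in TDR (184". Table 4 (biochemistry) puts the first day of LTS13769 at day 183. Table 3's Month 1 row (target 213) runs from the first LTS13769 day to day 228. The double-asterisk footnote under Table 3 gives an upper limit of 273 days, while the Week 27 row gives 198.

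**The concern.** The same named visit should have the same target day in every table, because the study-day origin is the same. Table 3 departs from the others without a stated reason. The departure matters most where two visits are only two weeks apart. Moving both targets about a week later moves the Week 25/27 boundary to day 183, close to where a Week 27 sample would be expected.

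At stake is the titer shown at the end of TDR12857. Protocol Section 11.5.5 promises titer summaries at each study visit, and SAP Section 2.4.5.6 adds graphs of titer over time. The same SAP section relates PK to the titer category at the time of the PK assessment and urinary Hex4 to the titer at a specified visit. Tables 5 and 6 centre Week 25 Hex4 and PK on day 169. If those pairings use analysis visits, a Week 27 titer could be set against Week 25 PK or Hex4.

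**Working it through.** **1. Reproduce the plan's boundary.** The midpoint of the Table 3 targets is (176 + 190)/2 = 183, the printed end of the Week 25 window.

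**2. Compare targets.** The reference days are Table 4 for Weeks 5 to 25 and Table 7 for Week 27.

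| Week | Table 3 target | Other tables | Difference | 7(n−1)+1 | Table 3 window |
|---|---|---|---|---|---|
| 5 | 35 | 29 | 6 | 29 | 23–50 |
| 9 | 63 | 57 | 6 | 57 | 51–78 |
| 13 | 91 | 85 | 6 | 85 | 79–106 |
| 17 | 119 | 113 | 6 | 113 | 107–134 |
| 21 | 148 | 142 | 6 | 141 | 135–163 |
| 25 | 176 | 169 | 7 | 169 | 164–183 |
| 27 | 190 | 184 | 6 | 183 | 184–198 |

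Days 29, 57, 85, 113, 141 (or 142) and 169 each fall inside the correct Table 3 window. Only Week 27 is at risk.

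**3. Assign Week 25 and Week 27 samples under rules 1 and 3.** The TDR12857 schedule is not in the documents, so three readings of on schedule are shown.

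- First infusion = day 1 (samples on days 169 and 183): both fall in 164–183. Distances to 176 are |169 − 176| = 7 and |183 − 176| = 7. Rule 3 takes day 183, so Week 25 shows the Week 27 titer and Week 27 is empty.
- First infusion = day 0 (days 168 and 182): distances are 8 and 6. Rule 1 takes day 182, with the same result.
- Targets printed in the other tables (days 169 and 184): day 184 falls in 184–198. Both samples are assigned correctly, provided LTS13769 has not started.

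**4. Allow for attendance (assumed).** Let each visit vary independently and uniformly by −3 to +3 days, giving 7 × 7 = 49 equally likely pairs. Ignore the cut at LTS13769 start.

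- Week 27 centred on 183: 28/49 = 57% of Week 27 samples fall in the Week 25 window. For Week 25 deviations of −3 to 0, four Week 27 days replace the true value; for +1, +2 and +3, the counts are 3, 2 and 1. Total 4×4 + 3 + 2 + 1 = 22, and 22/49 = 45%.
- Week 27 centred on 184: 21/49 = 43% enter the window. The counts are 3 for each of −3 to 0, then 2, 1 and 0. Total 4×3 + 2 + 1 + 0 = 15, and 15/49 = 31%.

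In the other 6 pairs of each case, Week 25 is kept but the Week 27 value drops out of the by-visit table. With ±7 days, window entry alone is 8/15 = 53% (centre 183) or 7/15 = 47% (centre 184).

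**5. Check the boundary with the extension.** With Table 4's first LTS13769 day of 183, the Week 27 window runs from 184 to 182 and is empty. The Week 25 row is not cut at LTS13769 start, so day 183 belongs to both the Week 25 window and the Month 1 window.

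**The case against.** Three points on the other side have force.

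First, day 183 is an assumption. The only other Week 27 target in Appendix B is day 184, and a sample on that day is assigned correctly before LTS13769 starts. A reader might infer that every on-schedule Week 27 sample overwrites Week 25. The documents do not support that, because the result turns on a single day and the TDR12857 schedule is not given.

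Second, a reader might infer a simple numbering slip, with day 7n used in place of 7(n−1)+1. That fits Weeks 5 to 17 only; 148, 176 and 190 are 7n+1. The extra day matters. A Week 25 target of 175 would put day 169 at distance 6 and day 183 at distance 8, and the true Week 25 value would be kept. What can be said is that the targets are 6 to 7 days later than in the other tables.

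Third, the reach is narrow. A reader might take this visit as the antibody reference point for entry to the extension. No section makes it so: SAP Sections 2 and 2.5.1 set baseline before the first TDR12857 dose, and Week 27 serves as a baseline for MRI only. In Sections 2.1.4.6 and 2.4.5.6, incidence, onset, duration, peak and last titer, ever-positive status and response class rest on samples, not analysis visits.

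These points limit the size and reach. They do not explain why Table 3 differs from its companion tables, and they leave the empty and overlapping windows at LTS13769 start untouched.

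**Conclusion.** The inconsistency holds and is visible on the face of the SAP. Applied as written, Table 3 labels any Week 27 antibody sample on or before day 183 as Week 25, and rules 1 and 3 then discard the true Week 25 value whenever the Week 27 sample is at least as close to day 176.

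The replacement rates of 45% and 31% rest on assumed uniform, independent variation of up to 3 days, and on Week 27 being centred on day 183 or 184. They illustrate the sensitivity; they are not estimates of attendance in this trial. The larger window-entry percentages should not be read as overwriting rates.

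This is a minor correction in a descriptive study: it changes the by-visit titer at one or two time points, and possibly the PK and Hex4 pairings if those are built on analysis visits. The main immunogenicity results are unaffected.

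**What to change.** Align the Table 3 targets with the other tables, at about days 29, 57, 85, 113, 141, 169 and 183, and recentre the windows on the midpoints. The Week 25/27 boundary becomes (169 + 183)/2 = 176, so Week 25 ends on day 176 and Week 27 runs from day 177 to day 198 or LTS13769 start. The printed 198 already equals (183 + 213)/2.

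Moving the targets is not enough. With the first LTS13769 day at 183, a Week 27 window cut on the day before would end at 182. A day-183 sample would then fall in Month 1, where a day-213 sample would displace it. So also:

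- cut the Week 25 row at LTS13769 start;
- assign an antibody sample drawn before the infusion on the first LTS13769 day to Week 27, not Month 1, so that no day belongs to two windows;
- change the footnote's 273 to match the row's 198.

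The cost is an edit to one SAP table and its footnote, with the matching change in the visit-assignment program. No new data are needed.
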